7.11 Criteria and Procedures for Withdrawal

A patient may decide to withdraw from the investigation at any time either before or after undergoing the procedure without prejudice or loss of care. The patient should notify the investigator of his/her desire to withdraw. The investigator will notify the sponsor. The investigator may also decide to withdraw the patient from the investigation at any time based on medical judgment. In these instances, the appropriate study visit and study termination data should be submitted to the data coordinating center, and will include the reason why the patient has been withdrawn from the study.

Patients who withdraw consent after treatment will be followed until the time of their withdrawal. No patient will be removed from the study unless the patient has withdrawn his/her consent before treatment or no treatment was ever attempted.

In the event a patient is lost to follow-up or cannot be contacted for post-treatment assessments, every effort will be made to locate the patient, and these efforts will be documented. If the patient cannot be located, a lost to follow-up entry will be submitted.

8 Deviations from Clinical Investigation Plan

Investigators are not allowed to deviate from this CIP without prior authorization by the sponsor except under emergency situations when necessary to preserve the rights, safety, and well-being of human subjects.

Deviations (failures to follow requirements of the CIP) and non-compliances (failures to follow applicable regulations) will be recorded together with an explanation. Deviations or non-compliances that impact the rights, welfare, or safety of patients shall be reported to the sponsor and IRB as required and as soon as possible.

If appropriate, corrective and preventive actions will be discussed by the sponsor, investigator, and/or the IRB to determine a suitable course of action.

9 Data Collection and Reporting

9.1 Electronic Case Report Forms (eCRF system)

Patient data will be collected and entered by the investigative site onto an electronic case report form (eCRF) through an electronic data capture (EDC) system. This is a secure, web-based system, allowing those with permission to access data from any location at any time. Source data are to be retained for data entered into the eCRF system. Site personnel are required to have

unique login names and passwords in order to enter patient data. In accordance with 21 CFR Part 11, the eCRF system creates a secure, computer-generated, time stamped audit trail to record the date and time of operator entries and actions that create, modify, or delete electronic records.

9.2 Data Reporting

Progress reports and a final report at the conclusion of the clinical investigation will be submitted by the investigators and sponsor to the IRBs as required by local regulations.

10 Data Management and Quality Assurance

10.1 Data Entry and Quality Assurance

Each principal investigator or appropriately trained designee shall enter the clinical data into the electronic data capture system. Investigators will provide all applicable clinical data and documentation to the sponsor. Patient data and documents pertaining to the investigation will be kept and archived by the sponsor. Data will be reviewed for missing data, data consistency, and reasonableness of responses. Discrepancies will be resolved through a formal query process involving direct contact with investigators or research coordinators. The data coordinating center is responsible for database management, data verification, and data archiving and retention.

As needed to assist the sponsor in its research (e.g., during evaluation of an adverse event), data will be accessible to the sponsor, the participating investigators, the manufacturer, and companies or individuals the sponsor authorizes.

10.2 Data Monitoring Arrangements

Written procedures for monitoring the investigation are maintained by the data coordinating center and can be found in Appendix B.

11 Safety Monitoring and Procedures for Reporting Adverse Events

11.1 Safety Monitoring

A Data Safety Monitoring Board (DSMB) consisting of independent physicians and at least one independent statistician, who are not investigators in the investigation, and who do not have a perceived conflict of interest with the conduct and administration of the investigation, will be convened on a regular basis to evaluate investigation progress and review adverse events.

Regularly scheduled review/monitoring of patient data will be conducted at the data coordinating center, in part, for identification of adverse events and assurance that they are correctly reported to the DSMB.

11.2 Adverse Event Reporting

Adverse events are to be reported to the data coordinating center using the appropriate case report form. In cases of adverse device effects or serious adverse events, completed forms should be submitted to the data coordinating center as soon as possible upon knowledge of the event.

The data coordinating center will review the information submitted for possible reporting to the sponsor. The sponsor shall, if required according to applicable regulations, report the event to the appropriate regulatory authority. If indicated, all investigators and sites will be notified by the sponsor. The investigator or designee will notify his/her IRB of applicable events according to institutional guidelines.

12 Early Termination or Suspension of the Investigation

Any decision to suspend enrollment or terminate the investigation will be made in conjunction with the sponsor, and the local IRB, if applicable. If a decision to terminate the study is made, all patients already treated will be followed for the duration of their participation in the study.

13 Ethical Considerations

The investigator is responsible for obtaining approval of this clinical investigation by the relevant IRB at his/her associated institution; the investigation will not begin until approval of the IRB has been obtained. The investigator is responsible for complying with requirements imposed by the IRB and/or regulatory authority. Furthermore, the investigator will ensure that regulations concerning the conduct of clinical data collection and data protection are followed.

14 Publication Policy

Publication policy, rights, and obligations for this investigation have been negotiated, detailed, and defined in the Investigation Contractual Documents and Agreements with the investigation site and investigators.

15 Trial Administration and Investigators

Contact information for the sponsor, data coordinating center, and monitor are provided in Appendix A.

15.1 Approvals and Agreements

The sponsor, coordinating investigator, and principal clinical investigators for each site shall agree to this document and any modifications. A justification for any modifications will be documented. Approval and agreement will be indicated by signing and dating the CIP signature page.

15.2 Investigators

A list including the coordinating investigator and principal clinical investigators along with their contact information and respective site information will be maintained at the data coordinating center and will be available upon request. All contact information will be updated periodically and maintained by the data coordinating center.

15.3 Insurance

Insurance for the study will be obtained by the sponsor prior to enrollment of the first patient.

[REDACTED]

[REDACTED]

[REDACTED]

[REDACTED]

[REDACTED]

[REDACTED]

[REDACTED]

[REDACTED]

[REDACTED]

[REDACTED]

[REDACTED]

[REDACTED]

[REDACTED]

[REDACTED]

[REDACTED]

APPENDIX B

Written Procedures for Monitoring Clinical Investigations

A. Selection of the monitor.

Designated by the sponsor to oversee the investigation, the monitor may be an employee of Cook, an employee of a monitoring organization (CRO), or an independent contractor or consultant. The monitor shall be qualified by training and experience to monitor the investigation in accordance with all applicable regulations and standards for conducting clinical investigations.

B. General duties of the monitor.

The monitor must ensure that the investigation is conducted in accordance with:

1. The signed investigator agreement.
2. The clinical investigation plan (CIP).
3. Any conditions imposed by the IRB or regulatory authority.
4. The requirements of the applicable regulations and standards.

C. Reports by the monitor to the sponsor.

1. Any non-compliance with the items listed above. In the event that the investigator is not complying with the requirements outlined above, it is the sponsor's responsibility to secure compliance.
2. Any adverse events or effects that are potentially reportable to a regulatory authority.

D. Initiating the investigation.

Prior to initiating any clinical use of the device, the monitor or sponsor representative will participate in a pre-investigation or initiation visit with each investigative site.

At a minimum, the following items shall be addressed during the site initiation visit:

- Provide training to investigator on his/her responsibilities per the investigator agreement, applicable laws, regulations, and standards; and
- Provide training to investigator that the IRB approval letter and informed consent/patient information is on file before initiation of the clinical investigation.

Additionally, training may be provided to the investigator on:

- The regulatory status of the device/product(s) and the requirements for the accountability of same;
- The nature of the CIP;
- The requirements for an adequate and well-controlled clinical investigation;

- His or her obligation to obtain informed consent in accordance with applicable regulations;
 - His or her obligation to ensure continuing review of the clinical investigation by the IRB in accordance with conditions of approval and applicable regulations and to keep the sponsor informed of such IRB approval and subsequent IRB actions concerning the investigation;
 - The importance of access to an adequate number of suitable subjects to conduct the investigation;
 - The importance of adequate facilities for conducting the clinical investigation; and
 - The importance of sufficient time from other obligations to carry out the responsibilities to which the investigator is committed by applicable regulations.
- E. During the course of the investigation, at the direction of the Project Manager, the monitor should visit the site frequently enough to ensure that:
- The facilities and research staff used by the investigator continue to be acceptable for purposes of the clinical investigation;
 - The applicable version of the CIP and agreements are being followed;
 - Changes to the CIP, informed consent/patient information have been approved by the IRB and/or reported to the sponsor and the IRB;
 - Accurate, complete, and current records are being maintained;
 - Accurate, complete, and timely reports are being made to the sponsor and IRB; and
 - The investigator is carrying out the agreed-upon activities and has not delegated them to other previously unspecified staff.
- As appropriate, the following tasks could be performed during periodic visits:
- Device/product accountability review;
 - Adverse event review to ensure that events are appropriately reported within the time periods required by the sponsor, CIP, IRB, and applicable regulatory requirements; and
 - Source data verification per the monitoring plan to determine that:
 - Informed consent/patient information has been documented in accordance with applicable regulations and expectations of the local IRB;
 - The information recorded in the case report forms (paper or electronic) is complete, accurate, and legible;
 - There are no omissions in the CRFs of specific data elements, such as the administration to any patient of concomitant test articles or the development of an intercurrent illness;

- Missing visits or examinations are noted; and
- Subjects failing to complete the clinical investigation and the reason for each failure are noted.

F. Records of the monitor.

The monitor shall prepare and maintain records of each initiation visit and each periodic visit, general site contact, or discussion. These will include:

1. Date, name, and address of the investigator, and names of other staff members present at each meeting.
2. A summary of the findings of the visit.
3. A statement of any action taken by the monitor or investigator to correct any deficiencies noted.
4. The monitor shall immediately notify the sponsor of any conditions of non-compliance with the CIP, conditions of IRB or regulatory authority approval, or the applicable regulations.

APPENDIX C

Definitions

Attempted stent removal/retrieval: an endoscopic procedure in which one of the following occurs:

- 1) Removal is attempted by grasping the green lasso or other portion of the stent with the intention to remove the stent, or
- 2) Removal is intended, but the subject is not considered to be a candidate for safe endoscopic stent removal (i.e. endoscopic removal is felt to be not possible or not safe)

Clinical success, for patients with obstruction caused by an intrinsic or extrinsic malignancy or patients with a refractory benign esophageal stricture: improvement or relief of dysphagia symptoms at the 7-day post-stent follow-up

Clinical success, for patients with a fistula, perforation, or leak: seal sufficient to enable oral intake at the 7-day post-stent follow-up

Dysphagia score: ■

- 0 = able to eat a normal diet
- 1 = able to eat some solid food
- 2 = able to eat some semi-solid food only
- 3 = able to swallow liquids only
- 4 = inability to tolerate any oral intake

Significant dysphagia ≥ 2

Dysphagia, improvement: a decrease in the dysphagia score by at least 2

Dysphagia, relief: complete relief of dysphagia (i.e., dysphagia score of 0)

Stent migration: migration of the stent such that it is no longer covering treated lesion

Stent removal-related adverse events: an adverse event directly related to the endoscopic removal of the stent. These events include esophageal perforation, esophageal tears, and esophageal bleeding requiring immediate intervention. If these conditions were present prior to stent placement, any worsening due to stent removal would be considered related to the removal procedure. However, an adverse event identified during the removal procedure that was not caused specifically by removing the stent will be reported separately. For example, an ulceration or perforation that arose during implantation would not be considered as associated with

removal. Also, events caused by either applying or removing a method of supplemental fixation will not be considered related to stent removal.

Successful stent removal: one in which the Evolution® Esophageal fully covered stent

- 1) Is completely removed from the patient during a single endoscopic procedure with the wire mesh integrity maintained such that the stent can be removed in one contiguous piece, and
- 2) Has no tissue damage or hemorrhage visible during the retrieval procedure that is both:
 - a. Related to endoscopic stent removal and
 - b. Requires immediate treatment

Technical success: a stent successfully delivered and placed at its intended location at the end of the procedure (note: adjustments made during the procedure are not considered a technical failure)

Definitions for the following terms are not provided in this CIP, but can be found in the applicable regulations:

- Adverse event
- Adverse device effect
- Device deficiency
- Serious adverse event
- Serious adverse device effect
- Unanticipated adverse device effect
- Unanticipated serious adverse device effect

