5.6 Variables to be Measured to Demonstrate Achievement of Endpoints

The primary endpoint will evaluate endoscopic removability of the Evolution® Esophageal fully covered stent. Specifically, the ability to completely remove the stent, incidence of tissue damage requiring immediate intervention, and hemorrhage requiring immediate intervention will be collected. Information regarding adverse events will be collected throughout this study during clinical assessments or telephone contact with the patients.

The clinical data will be collected on standardized case report forms. The schedule for assessments is summarized in Table 2 (section 7.6).

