6.3 Missing Data

[REDACTED]

Appropriate summary statistics will be presented for the 58 patient cohort, as well as all the enrolled patients when appropriate, based on available data. Patient withdrawals and lost to follow-up will be tabulated and assessed for their potential impact on the study results. Specifically, if any patients withdraw or become lost to follow-up prior to the analysis of the 58 patients with stent removal, then the primary endpoint will be examined for the sensitivity of the results on these missing data via tipping point analysis.

[REDACTED]

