6.5 General Analysis

The first 58 patients with attempted endoscopic stent removal (see Appendix C for definition) after an indwell time of at least 7 days, but no more than 6 months, will be included [REDACTED]. It is recognized that additional patients enrolled prior to the 58th attempted endoscopic stent removal may also have stent removal attempted prior to exiting the study. Those additional patients will be followed until reaching a study endpoint; however, these patients will not be initially included [REDACTED]

Secondary endpoints may be analyzed separately and/or together for those patients with attempted stent removal compared to those patients without attempted stent removal. [REDACTED]

Descriptive summaries will be provided where appropriate for each of the primary and secondary variables. In general, summaries will be complete over the total population. Continuous variable summaries will include the number of subjects (N), mean, standard deviation, minimum, and maximum. Categorical variable summaries will include the frequency and percentage of subjects who are in the particular category. In general, the denominator for the percentage calculation will be based upon the total number of subjects with the measurement for the total population and by treatment group, unless otherwise specified.

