¹ If a non-study stent is placed (e.g., inside the study stent or after study stent removal) or if the study stent is removed surgically, patient will exit the study immediately. If study stent is completely removed endoscopically and not replaced, patient will be followed for 30 days. If stent is not completely removed and non-study stent is not placed, patient will be followed until patient reaches 6-month follow-up or stent is completely removed.

² Additional endoscopy and/or radiographic assessment (e.g., X-ray) should be performed if clinically indicated (e.g., lack of marked improvement in dysphagia score, significant pain, suspected stent migration). Additional X-rays may be warranted in patients at higher risk for migration.

³ If stent placed for fistula, perforation, or leak, radiographic assessment (e.g., barium swallow) should be performed to confirm successful sealing of the lesion after stent implantation and to confirm lesion closure following stent removal.

⁴ Patient will be requested to provide information regarding clinical symptoms (e.g., dysphagia) and adverse event information since the last contact, if applicable, during each telephone contact and clinical visit during the patient’s study participation. Adverse events should also be reported upon awareness of the event if between telephone contacts and clinical visits.

For patients with a fistula, perforation, or leak, documentation of the original lesion closure should be obtained following stent removal (e.g., barium swallow), even if the original lesion is not identified using endoscopy at stent removal.

Additional endoscopy and/or X-rays should be performed according to standard of care if clinical symptoms persist/recur (e.g., lack of marked improvement in dysphagia score, significant pain, suspected migration). Additional X-rays may be warranted in patients at higher risk for migration (e.g., patients undergoing radiation/chemotherapy, patients with gastric surgery resulting in altered anatomy). Symptoms resulting in additional endoscopies should be recorded as adverse events.

At follow-up, the following information should be recorded, at a minimum:

- Dysphagia score
- Patient’s resumption of oral intake
- Current clinical symptoms (e.g., pain, nausea)
- Adverse events (including serious events) since last contact

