7.8 Stent Removal

Patients will have the stent removed when it is clinically indicated based on the physician’s clinical judgment. Please refer to the manufacturer’s IFU for information regarding stent removal. The indwell time may be different depending on the indication for stent implantation.

[REDACTED]

There is a lasso loop with a grasping feature on both ends of the stent to allow stent removal. If the stent is endoscopically removed, the patient will be followed for 30 days post-stent removal unless a new, non-study stent is placed. If the stent is removed surgically (e.g., during esophagectomy), the patient will exit the study immediately.

If the stent is unable to be completely removed during the initial removal procedure, the patient will continue to be followed until the stent (or remainder of the stent) is removed, until an additional stent is implanted, or for 6 months after the initial stenting procedure, whichever comes first.

If the stent is endoscopically removed, the following information should be recorded, at a minimum:

- Reason for removal
- Dysphagia score (prior to stent removal)
- Ability to completely remove stent
- Device integrity
- Adverse events since last contact and during removal procedure (including serious events and visible tissue damage or hemorrhaging requiring immediate intervention)

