7.10 Study Exit

A patient will be considered to have exited the study when one of the following has occurred:

- Voluntary withdrawal
- Lost to follow-up
- Death
- 30 days post endoscopic stent removal
- Stent is surgically removed (e.g., during esophagectomy)
- Non-study stent is implanted (e.g., inside study stent or after study stent is removed)
- 6 months if the stent has not been removed or replaced

After a patient exits the study, the physician may continue to follow the patient per the institution's standard of care. No additional data will be submitted to the data coordinating center once a patient has exited the study.

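### Could endoscopies where removal was intended but judged unsafe drop out of the primary endpoint because Section 7.8 words its record for removed stents?

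*Combined protocol and SAP*

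**What the plan says.** Appendix C gives two ways for an endoscopy to count as an attempted removal. In the first, the physician grasps the stent meaning to take it out. In the second, "Removal is intended, but the subject is not considered to be a candidate for safe endoscopic stent removal". Success, also in Appendix C, requires among other things that the stent "Is completely removed from the patient during a single endoscopic procedure with the wire mesh integrity maintained". Section 6.5 forms the primary cohort from "The first 58 patients with attempted endoscopic stent removal" within the 7-day to 6-month window and points to Appendix C for the meaning of attempt.

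On recording, four places matter.

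- Section 5.6 says that "the ability to completely remove the stent, incidence of tissue damage requiring immediate intervention" and hemorrhage needing immediate intervention will be collected. It does not make this conditional on the stent having come out.
- Section 7.8 introduces its list with "If the stent is endoscopically removed, the following information should be recorded, at a minimum". One item on that list is whether the stent could be completely removed. A separate paragraph covers a stent that cannot be fully removed at the initial procedure and keeps the patient in follow-up.
- Section 7.6 lists dysphagia score, oral intake, symptoms and adverse events at follow-up, and adds that "Symptoms resulting in additional endoscopies should be recorded as adverse events".
- Section 7.10 lists study exits, including "6 months if the stent has not been removed or replaced".

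Section 6.3 refers to the period "prior to the analysis of the 58 patients with stent removal", where Section 6.5 speaks of attempted removal.

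**The concern.** The second kind of attempt depends on what the physician meant to do, and the stent is still in place afterwards. Read literally, the lead-in to Section 7.8 does not reach it. The follow-up list in Section 7.6 has no item for an intended removal, Table 2 has a column for stent removal but none for attempts, and no exit reason marks such an event.

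If the event were not written down, the patient could go one of two ways. A later clean removal could be scored as a success, or the patient could leave with no recorded attempt and the next attempt would fill the place among the 58. Neither route can lower the observed success rate. The tipping-point analysis in Section 6.3 responds to withdrawal and loss to follow-up, so it would not catch the omission. Up to 130 − 58 = 72 enrolled patients (72/130 = 55%) may lie outside the cohort, which would make a missing failure hard to notice. The study is single-arm and unblinded, and the pass limit under an exact test leaves room for very few failures.

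**Working it through.** **Inputs.** The cohort of 58 is from Section 6.2 and the goal of 88% from Section 6.1.1. The visible text gives no test, alpha, assumed true rate or mix of failure types. The exact binomial test, the true rates and the unrecorded shares below are therefore assumptions. For the same reason, 58 cannot be reproduced from the plan's own sample-size inputs.

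**Step 1: the pass limit.** With X ~ Binomial(58, 0.88), the one-sided p-value for k successes is P(X ≥ k).

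| Successes | Failures | Exact p |
|---|---|---|
| 57/58 | 1 | 0.0054 |
| 56/58 | 2 | 0.0239 |
| 55/58 | 3 | 0.0710 |
| 54/58 | 4 | 0.1594 |

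At one-sided 0.025 or 0.05 the limit is two failures. A single missed failure in a three-failure result would move p from 0.071 to 0.024.

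**Step 2: effect of an unrecorded share f of failures.** If the patient is later scored a success, the apparent rate is p′ = p + (1 − p)f. If the patient is replaced, it is p″ = p / (1 − (1 − p)f). The chance of passing is P(X ≥ 56) at that rate. For p = 0.88 and f = 0.10, p′ = 0.88 + 0.12 × 0.10 = 0.892 and p″ = 0.88 / (1 − 0.012) = 0.8907.

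| True rate | f = 0 | f = 2%: success / replaced | f = 10%: success / replaced | f = 20%: success / replaced |
|---|---|---|---|---|
| 88% | 2.4% | 2.7% / 2.7% | 4.3% / 4.0% | 7.4% / 6.7% |
| 95% | 44.1% | 45.5% / 45.4% | 51.2% / 50.9% | 58.9% / 58.3% |
| 98% | 89.0% | 89.5% / 89.5% | 91.3% / 91.3% | 93.4% / 93.3% |

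The arithmetic is sound, but every column after f = 0 depends on a share that nothing in the documents supports.

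**Step 3: would the plan, as written, lose these events?**

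- *Section 5.6 against Section 7.8.* Section 5.6 makes removability a collected variable with no condition attached. A stent judged impossible or unsafe to remove is a removability outcome.
- *The Section 7.8 list against its own lead-in.* An item on whether the stent could be completely removed would carry almost no information if the list applied only to stents that came out. The list makes more sense as covering the removal procedure, with a loosely worded lead-in. It is also declared a minimum.
- *Procedures that leave the stent in.* Section 7.8 and footnote 1 of Table 2 both provide for incomplete removal with continued follow-up. The stent-removal column of Table 2, which calls for endoscopy and a clinic visit, is therefore not confined to successes.
- *Forming the cohort.* Sections 1, 5.1, 6.2, 6.5 and 7.4 all count attempts, and Section 6.5 ties the count to Appendix C. The cohort cannot be assembled as defined without asking whether each endoscopy met either part of that definition.
- *Exit list and the wording of Section 6.3.* An abandoned removal does not end participation, so it has no place in Section 7.10. The phrase in Section 6.3 is shorthand for the cohort that Section 6.5 defines in full.
- *Scoring.* Appendix C ties success to a single procedure and classes an abandoned removal as an attempt. Together these favor scoring that patient as a failure even if the stent comes out later, though no visible sentence says so outright.

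**The case for a change.** The strongest case for acting is that none of these provisions names intention. Section 5.6 and the Section 7.8 item ask whether the stent could be removed, and neither asks whether removal was planned and then given up. A planned removal in a symptom-free patient, abandoned on inspection, triggers no explicit item in the visible lists. The analyst cannot recover a failure that was never entered, and intention is hard to reconstruct afterwards. An omission also favors the device, and one missed failure can decide the result.

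Much of this stands. The Section 7.8 lead-in does not match Appendix C, and no visible sentence asks for a record of intention or of the reason for abandoning removal. But that describes where an instruction is absent from the visible text; it does not show that the data will be absent. Such fields normally sit on the case report form, which is not in the documents, and part of Section 7.8 is redacted just before the removal rules. Source data retention (Section 9.1), review and query of missing data (Section 10.1) and the monitoring checks in Appendix B give further chances to catch an omission, although none is aimed at this one.

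**Conclusion.** The concern does not call for a change to the plan. It identifies a wording mismatch and an unwritten recording detail, which a sponsor applying Section 6.5 with the Appendix C definition would have to settle in order to count to 58. The claim that recording begins only once a stent has been removed is too strong, given Section 5.6 and the content of the Section 7.8 list itself.

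The sensitivity of the result to one failure is real: p = 0.024 with two failures and 0.071 with three, assuming an exact one-sided test. The probability that a failure is missed is unknown. At a true 88%, the chance of passing would go from 2.4% to 2.7% if 2% of failures were unrecorded and later scored as successes, and to 4.3% if 10% were. These figures illustrate the mechanism and do not estimate a bias. The conclusion rests on reading Section 7.8 together with Section 5.6 and Appendix C, and on the case report form carrying the attempt definition that the analysis needs. The documents neither confirm nor contradict the latter.
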